10.2 ANALYSIS POPULATIONS

All subjects who provide informed consent are considered study participants. Study populations are defined as follows:

- Full analysis set population (FAS), including all subjects who were enrolled into the study and attended at least one post-baseline assessment.
- Per-Protocol Population (PP), including all subjects in the full analysis set who have no significant protocol deviations and met the inclusion/exclusion criteria.
- Safety Population (SAF), including all subjects who have received IP.

10.3 BASELINE DATA

Data to be summarised at baseline includes all collected demographic variable such as age, gender, primary diagnosis, height, weight, BMI, medical history and co-morbid conditions. The baseline variables will be used to describe the outcome data where necessary. Continuous baseline data will be summarized using frequency, means, and standard deviations, median, minimum and maximum. Categorical variables will be summarized using counts and percentages. The percentages will be calculated based on the number of non-missing values.

10.4 EFFICACY ANALYSIS

10.4.1 Analysis of Primary Endpoint

Clinical success rate, defined as subjects without a signs of failure and/or re-intervention at 6 months, surgeon assessment:

Study Protocol—Device	
Prospective, Multicenter, Post-Market Clinical Follow-up Study to evaluate safety and performance of the SUTUREFIX ULTRA and SUTUREFIX CURVED Suture Anchors in shoulder and hip arthroscopic repair	Number: 17-5010-06
	Version: 1.0, 09/MAY/2018
	Page: Page 47 of 87

- The frequency of the subjects without a signs of failure and/or re-intervention at 6 months together with percentage with a 95% CI will be reported. Clinical success rate for the entire sample, by device implanted (SUTUREFIX ULTRA and SUTUREFIX CURVED) as well as the position, i.e. the hip or the shoulder will be reported. A binary variable of success/failure will be used to fit a logistic model adjusting device implanted and position to estimate the odds ratio of success if data allows.

10.4.2 Analysis of Secondary Endpoint(s)

- Intra-operative anchor deployment success rate
- Number of anchors pulled out
- Use of additional anchors as a result of intra operative failure
- Device-related re-intervention

All the above variables will be categorical in nature hence frequencies together with percentages will be tabulated for the entire sample as well as by device implanted (SUTUREFIX ULTRA and SUTUREFIX CURVED) as well as the position, i.e. the hip or the shoulder will be reported.

All subjects

Clinical success rate, defined as subjects without signs of failure and/or re-intervention at 12 months; surgeon assessment

- The frequency of the subjects without a signs of failure and/or re-intervention at 12 months together with percentage with a 95% CI will be reported. Clinical success rate for the entire sample, by device implanted (SUTUREFIX ULTRA and SUTUREFIX CURVED) as well as the position, i.e. the hip or the shoulder will be reported. A binary variable of success/failure will be used to fit a logistic model adjusting device implanted and position to estimate the odds ratio of success if data allows.
- Subject pain assessed with a VAS at 6 months* and 12 months*

Study Protocol—Device	 smith&nephew
Prospective, Multicenter, Post-Market Clinical Follow-up Study to evaluate safety and performance of the SUTUREFIX ULTRA and SUTUREFIX CURVED Suture Anchors in shoulder and hip arthroscopic repair	Number: 17-5010-06
	Version: 1.0, 09/MAY/2018
	Page: Page 48 of 87

- Subject satisfaction assessed with a VAS at 6 months* and 12 months*
- EQ-5D Questionnaire at 6 months* and 12 months*
 - The VAS and EQ-5D-5L scores at different time points and end of study for the entire sample, by device implanted (SUTUREFIX ULTRA and SUTUREFIX CURVED) as well as the position, i.e. the hip or the shoulder will be summarized using mean, median, SD, minimum, and maximum. A one sample t-test will be used to test the difference between baseline and end of study scores. A non-parametric test will be considered if necessary.
- EQ-5D-5L

Based on the subjects responses (no problems/some or moderate problems/extreme problems) to each dimension (mobility, self-care, usual activities, pain/discomfort and anxiety/depression) an index utility score is calculated to represent the overall EQ-5D-5L score for each subject.

The subject responses to each dimension score and the overall EQ-5D-5L index utility scores and EQ VAS scores will be summarized at baseline and all post-operative visits for the entire sample, by device type implanted and as well as the position, i.e. the hip or the shoulder.. The change in EQ-5D-5L index utility score and the change in EQ VAS score between baseline and all post-op visits will also be summarised.

EQ-5D-5L Utility scores and EQ VAS scores will be assessed using separate repeated measures ANOVA model, with the relevant score as the dependent variable for on entire sample with device implanted and position accounted for as levels in the model.

Hip subjects

- Hip Outcome Score Activities of Daily Living (HOOS-ADL) at 6 months* and 12 months*

Study Protocol—Device	 smith&nephew
Prospective, Multicenter, Post-Market Clinical Follow-up Study to evaluate safety and performance of the SUTUREFIX ULTRA and SUTUREFIX CURVED Suture Anchors in shoulder and hip arthroscopic repair	Number: 17-5010-06
	Version: 1.0, 09/MAY/2018
	Page: Page 49 of 87

- Modified Harris Hip Score (HHS) at 6 months* and 12 months*
 - The HOOS and HHS scores at different time points and end of study will be will be summarized for the entire sample and device implanted using median, SD, minimum, and maximum. A one sample t-test will be used to test the difference between baseline and end of study scores.

Shoulder subjects

- ROWE Shoulder Scores at 6 months* and 12 months*
- ASES Shoulder Scores at 6 months* and 12 months*
- Complete Constant-Murley Score for shoulder* at 6 months* and 12 months*
 - The ROWE and Constant-Murley Shoulder scores at different time points and end of study will be will be summarized for the entire sample and device implanted using mean, median, SD, minimum, and maximum. A one sample t-test will be used to test the difference between baseline and end of study scores. A non-parametric test will be considered if necessary.

**Patient Reported Outcomes (PROs) are optional and used according to the surgeon's preference*

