Study Duration:	Study duration: 24 months Full analysis: after 12 month follow-up Enrollment period: 12 months
Primary endpoint:	
 Clinical success rate, defined as subjects without signs of failure and/or re-intervention at 6 months, as assessed by the surgeon
Secondary endpoint(s):	
 Clinical success rate, defined as subjects without signs of failure and/or re-intervention at 12 months, as assessed by the surgeon Intra-operative anchor deployment success rate Number of anchors pulled out Use of additional anchors as a result of intra operative failure Device-related re-intervention Safety evaluation at all time points Post-operative clinical success rate and performance assessed with subject reported outcomes as follows: 
 All subjects Subject pain assessed with a VAS at 6 months* and 12 months* Subject satisfaction assessed with a VAS at 6 months* and 12 months* EQ-5D Questionnaire at 6 months* and 12 months* Hip subjects Hip Outcome Score Activities of Daily Living (HOOS-ADL) at 6 months* and 12 months* Modified Harris Hip Score (HHS) at 6 months* and 12 months* Shoulder subjects ROWE Shoulder Scores at 6 months* and 12 months* ASES Shoulder Scores at 6 months* and 12 months* Constant-Murley Shoulder Score at 6 months* and 12 months* 
* Patient Reported Outcomes (PROs) are optional and used according to the surgeon's preference

Safety Data	AEs, SAEs, ADEs, SADE, USADEs

Suturefix Ultra Suture Anchor Suturefix Curved Suture Anchor	
Prospective, Multicenter, Post-Market 1 year Clinical Follow-up Study to evaluate safety and performance of the SUTUREFIX ULTRA and SUTUREFIX CURVED Suture Anchors in shoulder and hip arthroscopic repair	Number: 17-5010-06 Version: 1.0, 09/MAY/2018 Page: Page 9 of 87

STUDY SCHEMATIC (should be identical to Table 9.1.1-1)

Schedule of events (*as needed)	Visit 1	Visit 2	Visit 3 Visit	Visit 4 Telephone Call or Visit	Visit 5 Unscheduled Visit
	Pre-Operative	Operative through Discharge	6 Months (± 1 M)	12 Months (± 1 M)	
Informed Consent	√				
Inclusion/Exclusion Criteria	√				
Demographics/ Medical History	√				
Intra-operative failure as assessed by the surgeon		√			
Post-operative through Discharge		√			
Post-operative Repair failure			√	√	√
All subjects					
Pain assessment with VAS	√**		√**	√**	√**
Satisfaction assessment with VAS	√**		√**	√**	√**
EQ-5D questionnaire	√**		√**	√**	√**
Hip					

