9.1.2 Visit 1: Pre-Operative Visit

- Obtain written informed consent from the subject as detailed in Section 7.5
----- Do not proceed until consent has been obtained -----
- Obtain demographic information and medical history, including information on all concomitant medications/therapies
- Screen the subject for protocol inclusion/exclusion criteria
- Assign the subject a study number and instruct the subject on treatment procedures
- Complete Screening and Enrollment Log
- Complete VAS-Scale for Pain for all subjects*
- Complete EQ-5D questionnaire for all subjects*
- Complete ROWE Score for shoulder*
- ASES Score for shoulder*
- Complete Constant-Murley Score for shoulder*
- Complete HOOS-ADE Score for hip*
- Complete Modified HSS Score for hip*
- Perform MRI, only in case of repair failure
- If any adverse events are observed or reported, they must be recorded as instructed in Section 12.3, adverse events and device deficiencies
- Complete Pre-Operative Visit CRFs

**Patient Reported Outcomes (PROs) are optional and used according to the surgeon's preference.*

Study Protocol—Device	 smith&nephew
Prospective, Multicenter, Post-Market Clinical Follow-up Study to evaluate safety and performance of the SUTUREFIX ULTRA and SUTUREFIX CURVED Suture Anchors in shoulder and hip arthroscopic repair	Number: 17-5010-06
	Version: 1.0, 09/MAY/2018
	Page: Page 40 of 87

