9.1.4 Visit 3: 6-Month Follow-up Visit (\pm 1 month)

- Query subject regarding any changes in general health and the use of concomitant medications.
- If any adverse device effects or device deficiencies are observed or reported, they must be recorded as instructed in Section 12.3, adverse events and device deficiencies
- Post-operative repair failure
- Complete VAS-Scale for Pain and Satisfaction for all subjects*
- Complete EQ-5D questionnaire for all subjects*
- Complete ROWE Score for shoulder*
- ASES Score for shoulder*
- Complete Constant-Murley Score for shoulder*
- Complete HOOS-ADE Score for hip*

Study Protocol—Device	
Prospective, Multicenter, Post-Market Clinical Follow-up Study to evaluate safety and performance of the SUTUREFIX ULTRA and SUTUREFIX CURVED Suture Anchors in shoulder and hip arthroscopic repair	Number: 17-5010-06
	Version: 1.0, 09/MAY/2018
	Page: Page 41 of 87

- Complete Modified HSS Sore for hip*
- Perform MRI/Imaging only in case of repair failure
- Complete 6-Months Follow-up Visit CRFs
- Instruct the subject on follow-up procedures, including scheduling a FU call or visit in (\pm 1M) 12 months

**Patient Reported Outcomes (PROs) are optional and used according to the surgeon's preference.*

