21.3 QUALITY OF LIFE MEASURES EQ-5D-5L

Under each heading, please tick the ONE box that best describes your health TODAY.

MOBILITY

I have no problems in walking about
 I have slight problems in walking about
 I have moderate problems in walking about
 I have severe problems in walking about
 I am unable to walk about

SELF-CARE

I have no problems washing or dressing myself
 I have slight problems washing or dressing myself
 I have moderate problems washing or dressing myself
 I have severe problems washing or dressing myself
 I am unable to wash or dress myself

USUAL ACTIVITIES (e.g. work, study, housework, family or leisure activities)

I have no problems doing my usual activities
 I have slight problems doing my usual activities
 I have moderate problems doing my usual activities
 I have severe problems doing my usual activities
 I am unable to do my usual activities

PAIN / DISCOMFORT

I have no pain or discomfort
 I have slight pain or discomfort
 I have moderate pain or discomfort
 I have severe pain or discomfort
 I have extreme pain or discomfort

ANXIETY / DEPRESSION

[figure not shown]
I am not anxious or depressed
 I am slightly anxious or depressed
 I am moderately anxious or depressed
 I am severely anxious or depressed
 I am extremely anxious or depressed

Study Protocol—Device	
Prospective, Multicenter, Post-Market Clinical Follow-up Study to evaluate safety and performance of the SUTUREFIX ULTRA and SUTUREFIX CURVED Suture Anchors in shoulder and hip arthroscopic repair	Number: 17-5010-06
	Version: 1.0, 09/MAY/2018
	Page: Page 68 of 87

- We would like to know how good or bad your health is TODAY.
- This scale is numbered from 0 to 100.
- 100 means the best health you can imagine.
0 means the worst health you can imagine.
- Mark an X on the scale to indicate how your health is TODAY.
- Now, please write the number you marked on the scale in the box below.

YOUR HEALTH TODAY =

I

[figure not shown]
Study Protocol—Device	 smith&nephew
Prospective, Multicenter, Post-Market Clinical Follow-up Study to evaluate safety and performance of the SUTUREFIX ULTRA and SUTUREFIX CURVED Suture Anchors in shoulder and hip arthroscopic repair	Number: 17-5010-06
	Version: 1.0, 09/MAY/2018
	Page: Page 69 of 87

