21.4 ADDITIONAL ASSESSMENTS

Patient Hip Assessments

Pain Assessment

1. Please select a number from the scale below that indicates the level of pain you are experiencing from your hip today

[figure not shown]

*Please comment below

*Please provide a reason for your score _____

Patient Satisfaction

2. Please select a number from the scale below that indicates your level of satisfaction with the arthroscopy repair surgery to stabilize your hip

*Please comment below

*Please provide a reason for your score _____

Study Protocol—Device

Prospective, Multicenter, Post-Market Clinical Follow-up Study to evaluate safety and performance of the SUTUREFIX ULTRA and SUTUREFIX CURVED Suture Anchors in shoulder and hip arthroscopic repair

[figure not shown]
Number: 17-5010-06

Version: 1.0, 09/MAY/2018

Page: Page 70 of 87

Patient Shoulder Assessments**Pain Assessment**

1. Please select a number from the scale below that indicates the level of pain you are experiencing from your shoulder today

*Please provide a reason for your score _____

Patient Satisfaction

2. Please select a number from the scale below that indicates your level of satisfaction with the arthroscopy repair surgery to stabilize your shoulder

*Please provide a reason for your score _____

Study Protocol—Device	 smith&nephew
Prospective, Multicenter, Post-Market Clinical Follow-up Study to evaluate safety and performance of the SUTUREFIX ULTRA and SUTUREFIX CURVED Suture Anchors in shoulder and hip arthroscopic repair	Number: 17-5010-06
	Version: 1.0, 09/MAY/2018
	Page: Page 71 of 87

Hip dysfunction and Osteoarthritis Outcome Score (HOOS), English version LK 2.0

1

HOOS HIP SURVEY

Today's date: _____ / _____ / _____ Date of birth: _____ / _____ / _____

Name: _____

INSTRUCTIONS: This survey asks for your view about your hip. This information will help us keep track of how you feel about your hip and how well you are able to do your usual activities.

Answer every question by ticking the appropriate box, only one box for each question. If you are uncertain about how to answer a question, please give the best answer you can.

Symptoms

These questions should be answered thinking of your hip symptoms and difficulties during the **last week**.

S1. Do you feel grinding, hear clicking or any other type of noise from your hip?

Never	Rarely	Sometimes	Often	Always
				

S2. Difficulties spreading legs wide apart

None	Mild	Moderate	Severe	Extreme

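### Section 10.4.2 puts satisfaction with surgery under a baseline test and describes the EQ-5D-5L index from three response levels instead of five; the 12-month Constant-Murley score also lacks a rule for telephone contacts

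*Combined protocol and SAP*

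**What the plan says.** **Satisfaction.** Section 10.4.2 lists the pain VAS, the satisfaction VAS and the EQ-5D one after another. It then covers them with a single analysis paragraph that opens "The VAS and EQ-5D-5L scores at different time points and end of study for the entire sample" and continues "A one sample t-test will be used to test the difference between baseline and end of study scores". The hip item in section 21.4 asks for the number that "indicates your level of satisfaction with the arthroscopy repair surgery to stabilize your hip", and the shoulder item is worded in parallel. The row "Satisfaction assessment with VAS" is ticked at Visit 1 in the synopsis schematic and again in Table 9.1.1-1. The Visit 1 procedures in section 9.1.2 say only "Complete VAS-Scale for Pain for all subjects", whereas the 6-month procedures in section 9.1.4 say "Complete VAS-Scale for Pain and Satisfaction for all subjects".

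**EQ-5D-5L.** Section 10.4.2 introduces the index with "Based on the subjects responses (no problems/some or moderate problems/extreme problems) to each dimension". The form in section 21.3 offers five answers per dimension, including "I have severe problems in walking about" as an answer separate from being unable to walk about.

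**Constant-Murley.** Section 9.1.5 allows the 12-month contact to be a call or a visit and lists the Constant-Murley and Rowe scores there without separating the two modes. Section 10.4.2 tests both scores from baseline to end of study. Section 4.1 says that 35 of the 100 Constant points come from the patient's own rating.

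**The concern.** A change from baseline needs a baseline that means something. Satisfaction with an operation cannot be rated before the operation, so a pre-operative value could only reflect expectation or a misunderstanding of the question. The plan also gives sites two incompatible instructions for Visit 1.

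The EQ-5D-5L index enters the baseline test, the change summaries and a repeated measures ANOVA. A scoring description that does not match the form should not be carried forward into the SAP.

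For the Constant-Murley score, a telephone contact cannot supply the measured items. Without a stated rule, 12-month totals from phone contacts could be partial, estimated or missing, and the report would not show which.

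**Working it through.** The plan gives no figure of its own on this point, so the check is a comparison of texts with a few counts.

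**(a) Satisfaction**

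- Scope of the test: the analysis paragraph follows the pain and satisfaction bullets directly and excludes neither. It is unlikely to mean only the EQ-5D's own scale, because section 10.4.2 names the EQ VAS separately when it means that.
- Schedule tables with satisfaction ticked at Visit 1: 2 of 2. Mentions of satisfaction in section 9.1.2: 0. Sections 9.1.4 to 9.1.6 list pain and satisfaction together, so the visit text treats satisfaction as post-operative.
- If sites follow the tables, a baseline value exists but rates surgery not yet done, and the test uses it.
- If sites follow section 9.1.2, there is no baseline value and the test cannot run for satisfaction.

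Neither route gives a usable result.

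**(b) EQ-5D-5L**

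- Levels in the analysis text: none, some or moderate, extreme = 3.
- Levels on the form: none, slight, moderate, severe, unable or extreme = 5, in each of 5 dimensions.
- Possible health profiles: 3^5 = 243 under the text, against 5^5 = 3125 under the form.
- In the three-level text *severe* has no category, and *slight* is at best merged with *moderate*. No value set is named.

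**(c) Constant-Murley**

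- Points not rated by the patient, from section 4.1: 100 - 35 = 65 of 100.
- Items on the section 21.4 form that clearly need measurement: item 4 (abduction strength in pounds), item 5 (forward flexion in degrees) and item 6 (lateral elevation in degrees) = 3 of 8. Items 7 and 8 are hand positions and are not counted.
- The form as supplied shows no point values, so the 65 points cannot be assigned to those 3 items. The two figures are separate indications.
- Section 9.1.3 has subjects return to the facility for Visit 3, so the 6-month score can be obtained by examination. Section 9.1.4 tells sites to schedule a call or a visit for 12 months.
- The modified Harris Hip worksheet in section 21.4 makes the total null if any of questions 1 to 8 is missing. The Constant form shows no such rule.
- Number affected: unknown. Section 7.1 plans 40 shoulder subjects as a minimum, but the documents give neither the share followed by phone nor the uptake of the optional scores.

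**The case against.** The strongest reply is that these are optional, exploratory outcomes and that section 10 promises a fuller SAP before database lock. That limits the consequence, but nothing in the supplied text resolves the points, and a SAP alone does not correct the table that sites follow at Visit 1.

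On (a), the analysis sentence does not name satisfaction, the endpoint lists give it at 6 and 12 months only, and the Visit 1 tick is marked optional. However, pain is listed in the same way and is plainly meant to be tested from baseline, so the endpoint lists do not take satisfaction out of the test. It is true that no wrong result arises if section 9.1.2 is followed, but the prespecified test then has no data for satisfaction.

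On (b), a reader might infer that the trial will collect or score three-level data. The documents do not support that: the instrument is called EQ-5D-5L throughout, the five-level form is appended, and no three-level value set is specified. The defect is in the wording.

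On (c), a reader might infer that the 12-month Constant-Murley analysis is invalid. It is not: the visit option remains open, and the test is sound for subjects examined in person. What is missing is a handling rule. The Rowe motion section needs one on the same basis. Neither form names a rater, so that does not separate the two scores; the difference is that the Constant form asks for pounds and degrees.

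Nor is the one-sample t-test itself at fault, since applied to within-subject differences it is a legitimate choice.

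**Conclusion.** The point holds in three parts of unequal weight.

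- Part (a) is wrong as written and is the main finding. It rests on reading the VAS sentence as covering both scales listed immediately above it.
- Part (b) is a definite mismatch, 3 levels against 5, that calls for a text correction.
- Part (c) is a smaller gap: a score with measured items is listed at a contact that may be by telephone, with no rule for subjects who are phoned. Its size cannot be stated from the documents.

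The effect stops at optional, exploratory secondary outcomes. The primary endpoint, surgeon-assessed clinical success at 6 months, uses none of these scores and is not affected. The corrections should still be made before the SAP is finalised.

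**What to change.** - **(a)** Remove the Visit 1 satisfaction tick from both schedule tables. In the SAP, exclude satisfaction from the baseline test and summarise it at 6 and 12 months only. The table correction is a protocol amendment under section 15. It needs signatory and IRB/IEC approval, and that section reserves amendments after study start for exceptional cases, so it can reasonably travel with the next amendment. The analysis change is SAP wording.
- **(b)** Replace the three-level wording with the five levels in section 21.3, and score the index with a five-level value set named in the SAP. The cost is SAP wording.
- **(c)** In the SAP, use the 12-month Constant-Murley total only for subjects examined in person, report how many were followed by phone, and report the change from baseline to 6 months alongside it. State on the same basis how the Rowe motion section is handled for phone contacts. This requires contact mode to be available from the CRF or source records. The documents do not say that it is captured, so this must be checked and, if necessary, added. The statistical cost is a smaller and possibly selected 12-month sample; reporting the number phoned makes that visible.

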7. SUBJECT ENROLLMENT AND WITHDRAWAL

7.1 SUBJECT POPULATION

In this study a minimum of 80 subjects will be enrolled, 40 subjects for each group, hip and shoulder. The subjects will be treated with the study device(s) for hip or shoulder instability.

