9.1.5 Visit 4: 12-Months Follow-up Call or Visit (\pm 1 month)

- Query subject regarding any changes in general health and the use of concomitant medications.
- If any adverse device effects or device deficiencies are observed or reported, they must be recorded as instructed in Section 12.3, adverse events and device deficiencies.
- Post-operative repair failure
- Complete VAS-Scale for Pain and Satisfaction for all subjects*
- Complete EQ-5D questionnaire for all subjects*
- Complete ROWE Score for shoulder*
- ASES Score for shoulder*
- Complete Constant-Murley Score for shoulder*
- Complete HOOS-ADE Score for hip*
- Complete Modified HSS Sore for hip*
- Perform MRI/Imaging only in case of repair failure

**Patient Reported Outcomes (PROs) are optional and used according to the surgeon's preference.*

Study Protocol—Device	 smith&nephew
Prospective, Multicenter, Post-Market Clinical Follow-up Study to evaluate safety and performance of the SUTUREFIX ULTRA and SUTUREFIX CURVED Suture Anchors in shoulder and hip arthroscopic repair	Number: 17-5010-06
	Version: 1.0, 09/MAY/2018
	Page: Page 42 of 87

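### The repeated measures ANOVA for EQ-5D-5L utility and EQ VAS is left unspecified although the scores are optional at every visit; in its classical form it would drop subjects with partial data.

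*Combined protocol and SAP*

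**What the plan says.** Section 10.4.2 plans the following for the two EQ-5D scores: "EQ-5D-5L Utility scores and EQ VAS scores will be assessed using separate repeated measures ANOVA model". Each model is to cover hip and shoulder subjects together, and its only named factors are the anchor type and the joint. No SAS procedure, estimation method, covariance structure or missing-score rule is given. The only statement on missing values, in section 10.3, concerns the denominator of baseline percentages.

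The scores themselves are optional. The footnote to section 10.4.2 reads "Patient Reported Outcomes (PROs) are optional and used according to the surgeon's preference". It applies to "EQ-5D Questionnaire at 6 months* and 12 months", and the same footnote marks the baseline entry "Complete EQ-5D questionnaire for all subjects" in section 9.1.2. The 12-month contact may be by telephone ("9.1.5 Visit 4: 12-Months Follow-up Call or Visit").

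The same part of the plan also calls for:
- summaries of both scores at baseline and at every post-operative visit, and of the change between baseline and each of those visits;
- a one-sample t-test of baseline against end of study.

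Section 10 describes itself as brief and defers detail to a SAP to be completed before database lock. Section 10.1 makes all tests exploratory.

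**The concern.** The classical form of repeated measures ANOVA, with one row per subject and one column per visit, needs a score at every visit. A subject with baseline and 6-month scores but no 12-month score is left out entirely. That sits badly with two other rules of the plan. Section 10.2 admits to the full analysis set anyone enrolled with at least one post-baseline assessment, and section 7.8.4 allows data collected before withdrawal to be used.

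Optional collection at three visits makes incomplete records plausible, and section 7.7 expects some late or missed follow-up. With about 80 subjects, discarding observed visits could cost noticeable precision. Because the text does not say how the model is fitted, two analysts following it could report on different sets of subjects.

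**Working it through.** **The plan's own figure.** None exists for EQ-5D. The only sample-size figure (section 11: n = 40, 89%, half-width 11 points, 55% probability) concerns the primary endpoint. It reproduces: with Clopper-Pearson limits, a half-width of at most 0.11 needs at least 36 of 40 successes, and P(X ≥ 36 | n = 40, p = 0.89) = 0.547. It does not bear on this point.

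**Inputs.** N = 80 (section 7.1: "In this study a minimum of 80 subjects will be enrolled, 40 subjects for each group, hip and shoulder"). Three scheduled EQ-5D visits (section 9.1). Up to 8 sites (section 8.1). The missing rate is not documented, so it is assumed.

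**Scenario A: scattered gaps.** Let c be the probability that a score is present at a visit, independent across visits.

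- Complete at all three visits: 80c³
- At least two of three: 80[c³ + 3c²(1−c)]
- Baseline and 12 months both present: 80c²
- Observed scores: 240c; scores used by a complete-case analysis: 240c³

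| Missing per visit | Complete | At least two | Baseline + 12 m | Scores used / observed |
|---|---|---|---|---|
| 10% | 80 × 0.729 = 58 | 80 × 0.972 = 78 | 80 × 0.81 = 65 | 175 / 216 |
| 20% | 80 × 0.512 = 41 | 80 × 0.896 = 72 | 80 × 0.64 = 51 | 123 / 192 |
| 30% | 80 × 0.343 = 27 | 80 × 0.784 = 63 | 80 × 0.49 = 39 | 82 / 168 |

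**Precision.** Three normal visits were simulated (N = 80, correlation 0.5 and 0.7, 300 runs each). The contrast was 12 months minus baseline, estimated from complete cases and by maximum likelihood with unstructured covariance on all observed scores. The ratio of variances, likelihood to complete-case, was 0.84-0.89, 0.66-0.68 and 0.55-0.63 at 10, 20 and 30% missing. With 300 runs these are approximate.

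**Against the planned t-test.** The t-test uses the 80c² pairs, so its variance is about 80c³ / 80c² = c times the complete-case variance: 0.9, 0.8 and 0.7. Relative to that test the mixed model has about
- 10%: 0.84/0.9 to 0.89/0.9 = 0.93 to 0.99
- 20%: 0.66/0.8 to 0.68/0.8 = 0.83 to 0.85
- 30%: 0.55/0.7 to 0.63/0.7 = 0.79 to 0.90

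times the variance. Part of the loss is therefore already avoided elsewhere in the plan.

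**Scenario B: whole sites without EQ-5D.** With k of 8 equal sites not using it, 80 − 10k subjects remain: 60 for k = 2, 40 for k = 4. Both methods use the same subjects, and the variance ratio is 1.00.

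**Bias.** When 20-30% of 12-month scores were missing depending on the 6-month score, the complete-case mean at 12 months was too high by about 0.09-0.19 SD; the likelihood-based mean was within about 0.01 SD. The change from baseline was not biased under either method in this setting.

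**The case against.** The strongest reply is that no wrong analysis has been shown. In SAS, a repeated measures ANOVA model can be fitted as a mixed model that keeps partial records. A reader might infer that the plan commits to dropping incomplete subjects; the text does not say so, and a detailed SAP is still to come. This stands: the defect is that the text permits the classical form, not that it requires it.

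Second, a reader might infer that EQ-5D scores will often be missing, especially after a telephone contact. No rate is given, and section 9.1.5 lists EQ-5D under call or visit alike. The form in appendix 21.3 is self-completed and no telephone version is described, so gaps are foreseeable, but how many cannot be stated.

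Third, the footnote ties use to the surgeon's preference, which points to whole subjects, surgeons or sites without scores. There the change of model recovers nothing. This also stands.

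Fourth, the summaries of change by visit and the baseline-to-end test do not need three visits, so a claim that quality-of-life change would be estimated only in completers goes too far. Nor do the documents show that completers differ from the rest.

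Finally, it is tempting to say that a mixed model costs nothing. It needs a missing-at-random assumption and a covariance choice, with small-sample degrees of freedom at this size.

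**Conclusion.** The point holds as a minor one. The plan names a model whose classical form excludes subjects missing any one visit, for scores that are optional at all three visits, and says nothing on how it is fitted or how missing scores are handled. Under scattered missingness of an assumed 10-30% per visit, complete cases fall to 58-27 of 80, and a likelihood-based model reduces the variance of the 12-month change by roughly 11% to 45% compared with complete cases (ratios 0.89 to 0.55). Compared with the planned t-test the reduction is smaller, roughly 1% to 21%. If the missingness is by site or surgeon, the benefit is nil.

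These sizes rest on assumed rates, independence between visits, and correlations of 0.5 and 0.7. The benefit is mainly precision. The simulation shows some protection against bias in the 12-month mean but none needed for the change, and other dropout patterns were not examined. The endpoint is secondary and exploratory, so the study's main conclusion is not affected.

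**What to change.** In the SAP, replace the ANOVA with a linear mixed model for repeated measures, fitted separately to EQ-5D-5L utility and EQ VAS:

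- all available scheduled visits (baseline, 6 and 12 months), with unscheduled visits left out of the model;
- fixed effects for visit, position, device and visit-by-position;
- REML, unstructured covariance, Kenward-Roger degrees of freedom;
- change from baseline at 6 and 12 months with 95% CI.

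State the missing-at-random assumption, report EQ-5D completion by site and visit, and state that the model does not correct selection by surgeon preference. The SAP should also say how a subject who receives both anchors is classified for the device term, since the synopsis and section 8.1 allow both. Keep the planned summaries by visit and the t-test. Mixed models for the joint-specific scores are optional and correct no identified error.

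The cost is a paragraph of SAP text and a little more SAS work, with no new data. The downside is reliance on missing at random and on a covariance choice.
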